1. Baduanjin qigong is more effective than no-intervention control in (i)reducing cancer-related symptoms and symptom distress, (ii)improving mental health, (iii)enhancing quality of life, (iv)positively altering biomarkers, (v)enhancing mindfulness level.

- 2. Mindfulness meditation is more effective than no-intervention control in similar areas and directionality as the above (i) to (v).
- 3. There would be commonalities and differences between Baduanjin qigong and Mindfulness meditation in a)type of outcome variables, b)magnitude of change, c)time when significant outcomes emerge, d)frequency and length of self-practice and long-term compliance.
- 4. The associations among physical and psychological variables as well as psychophysiological biomarkers and the changes of such associations across the time points are exploratory.

Research Plan and Methodology

Research design

This study will utilize a 3-arm randomized controlled trial design with waitlist control. A conceptual model is provided in Appendix A. Upon recruitment, participants will be screened according to the inclusion and exclusion criteria (Appendix B). Baseline data will then be collected. Subsequently, eligible participants will be randomly assigned into one of the 8-week (i)Baduanjin qigong group, (ii)Mindfulness meditation group, and (iii)Waitlist Control group. The Waitlist Control group will continue to receive routine medical care and will have the option to attend either of the interventions after the study is completed. Participants from all 3 arms will be assessed on 4 time points (i)baseline prior randomization, (ii)mid-intervention (4th week), (iii)post intervention (8th week), (iii)6 months post-intervention. Participants will complete the study in 8 months.

Sample size determination, Participant eligibility and Recruitment

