To achieve a statistical power of 0.8 with medium effect size (f2 = 0.25) and significance level of 0.05 in repeated measures MANOVA under the proposed 3-group, 4-time point design, a sample size of 126 is needed. Assuming an attrition rate of about 33.5%, based on prior trials on cancer patients using qigong[8], recruitment of 189 participants (63 per arm) is required. The study population will consist of 189 Chinese-speaking patients aged between 18 and 74, diagnosed with colorectal cancer. Participants will be recruited via posters and newsletters put up at hospital and community organizations servicing cancer patients including Hong Kong Anticancer society. Recruitment will also be done via referral from oncologists. Screening will be conducted after recruitment by a trained research assistant or by the referring medical professional based on the inclusion and exclusion criteria listed in Appendix B.

Intervention groups

Both intervention groups will consist of 8 weekly 90-minute sessions, with a total of 12 contact hours. Interventions will be held in groups of about 10 participants led by 2 trainers qualified for the respective intervention form, one of whom will also be a mental health professional.

a) *The Baduanjin qigong Intervention*[61] consist of eight sequential forms of movements which is practiced with guidance on rhythmic breathing and mindful awareness (see Appendix C for details). Each cycle of the eight movements requires 10 to 15 minutes for completion. Four

cycles will be practiced in each session with short breaks arranged between them. In addition to the in-session practices, participants are encouraged to practice Baduanjin qigong for at least 20 minutes each day and keep a record of their daily practice in a log book.

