(b) *The Mindfulness meditation Intervention* which has been used by co-Is ([name] and [name]) in previous studies is developed based on the core components of the established Mindfulness-Based Stress Reduction and the Mindful Self-Compassion program with adaptation for local practice[57, 62]. The focus of the group is to nurture mindful awareness, acceptance, and self-compassion. The group sessions are composed of a combination of mindfulness-based practice, relaxation, and yoga exercise (Appendix D). The basic philosophy of this intervention is the emphasis of the nurturing of self-kindness attitude, and non-attachment attitude towards inter-personal connectedness and letting go of self-criticism, need for control, and defensive separation in times of adversity. Short breaks will be arranged between each practice. Adjuvant to the in-session practices, participants are recommended to practice the mindful techniques every day for at least 20 minutes while keeping a record of their practice.

(c) Waitlist control group members will continue with routine care and can join either the Baduanjin or Mindful intervention after the 6-month post-intervention assessment.

Ethics

This study will be reviewed by the HKU/HA Institutional Review Board. Written informed consent will be obtained from all participants. To ensure confidentiality, codes will be used to replace names. All data collected will be kept in locked spaces and destroyed 3 years after the study ends. The study will also be registered with the Hong Kong clinical trial registry.

Measurements

Assessments pertain to areas of (i)cancer-related symptoms and symptom distress, (ii)mental health, (iii)quality of life, (iv)biomarkers, (v)mindfulness, (vi)compliance, and (vii)demographic and clinical details. Self-rated scales and salivary cortisol are administered by participants themselves while blood pressure would be measured by the trained research assistant blinded to the randomization. Measurements are taken at all time points except demographic and clinical details.

Cancer-related symptom, symptom distress and quality of life

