1. Effectiveness of Baduanjin qigong and Mindfulness meditation (Objective 1 & hypotheses 1&2)

Analysis of variance and chi-square independence tests will be carried out using SPSS to compare the demographic profile of the three groups. The study will use latent growth modeling (LGM) in Mplus 7 [71] to explore the effectiveness of the two mind-body interventions over the four assessment time points, between the respective experimental and waitlist control groups. Traditional analytic techniques such as ANOVA or MANOVA adopt traditional deletion or substitution methods and may not yield precise estimates in the presence of missing data. LGM flexibly analyzes the overall population trajectories using nonlinear modeling such as quadratic growth and the between-person variation in outcome variables, thus allows analysis of all available data via full information maximum likelihood under missing-at-random assumption. This matches the standard intent-to-treat analytic approach of clinical trials with missing data. The level of statistical significance is set at p=0.05, with p-values greater than 0.05 but smaller than 0.10 taken as marginal significance. All models are estimated using the robust maximum likelihood estimator.

2. Commonalities and Differential effectiveness for Baduanjin qigong and Mindfulness meditation (Objective 2 and hypothesis 3).

To examine the commonalities and differential effectiveness for Baduanjin qigong and Mindfulness meditation, treatment effects of the two interventions are directly compared in multigroup conditional growth models. The linear slope factors of the outcomes are contrasted across the two intervention groups via computing the difference in the intercepts of the slope factors between two groups using Model Constraint option. Demographic and clinical characteristics that differed significantly across the three groups in the preliminary analysis are entered as covariates. Influential confounding variables such as clinical prognosis or frequency, intensity and duration of maintenance (compliance) of practice will be controlled.

3. The Mind-body correlations reflected in symptoms and psychophysiological markers (Objective 3 and hypothesis 4).

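### Both active arms are taught in groups of about 10, but no analysis allows for delivery group; if group members change alike, the planned standard errors are too small, by an amount the documents cannot fix.

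*Combined protocol and SAP*

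**What the plan says.** Allocation is by individual (Research design): "eligible participants will be randomly assigned into one of the 8-week (i)Baduanjin qigong group" or one of the other two arms. Delivery is in classes (Intervention groups): "Interventions will be held in groups of about 10 participants led by 2 trainers qualified for the respective intervention form". The control arm is not grouped (Intervention groups, item c): "Waitlist control group members will continue with routine care".

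On numbers, the sample size section states that "recruitment of 189 participants (63 per arm) is required". It names power, effect size, significance level, design and attrition, but no ICC or design effect.

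On analysis, Data analyses 1 compares each active arm with waitlist by latent growth models: "All models are estimated using the robust maximum likelihood estimator". Data analyses 2 compares the active arms: "The linear slope factors of the outcomes are contrasted across the two intervention groups". The groups in those multigroup models are the trial arms. The covariates are demographic and clinical characteristics, prognosis and practice compliance. Delivery group and trainer are not among them. The only nesting modelled, in Data analyses 4, is cortisol samples within participants, so the participant is the top level.

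**The concern.** Members of one class share eight 90-minute sessions and the same two trainers, so their changes may be correlated. Randomising individuals does not remove correlation that arises after allocation. Because only the active arms are grouped, the design is partially nested. An analysis that treats every participant as independent then leaves the effect estimates unbiased but understates their standard errors.

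Baseline is measured before randomisation, so the correlation that matters is in change, not in level. Exposure is greatest for qigong versus mindfulness (Primary objective 2), where both sides are grouped. The plan also labels p-values between 0.05 and 0.10 as marginally significant, so understated standard errors matter at that threshold too.

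The robust estimator looks like an answer but is not. Robust maximum likelihood allows for correlation within clusters only if it is told what the clusters are, and the plan names none.

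**Working it through.** **1. The plan's own figure.** A Pillai-trace MANOVA with 3 groups, 4 responses and f = 0.25 has df1 = 8, df2 = 2 × (126 − 5) = 242 and noncentrality 2 × 126 × 0.0625 = 15.75. Power is 0.807, and 126 is the smallest multiple of 3 that reaches 0.80. Then 126 / (2/3) = 189; the stated 33.5% gives 126 / 0.665 = 189.5. The formula treats participants as independent, so nothing is reserved for clustering. (The match needs f = 0.25 rather than f² = 0.25, a separate matter.)

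**2. Groups.** 63 / 10 = 6.3 groups per active arm. Completers: 126 / 3 = 42 per arm, and 42 / 6.3 = 6.7 per group. I use 6 groups of m = 7.

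**3. ICC applied directly to the quantity tested (for example week-8 change).** DEFF = 1 + (m − 1) × ICC. The ratio of true to planned standard error is √DEFF head to head and √((1 + DEFF)/2) against waitlist. Alpha = 2 × (1 − Φ(1.96 / ratio)). The ICCs are assumed.

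| ICC | DEFF | SE ratio, head to head | Alpha | SE ratio, vs waitlist | Alpha |
|---|---|---|---|---|---|
| 0.01 | 1.06 | 1.030 | 5.7% | 1.015 | 5.3% |
| 0.05 | 1.30 | 1.140 | 8.6% | 1.072 | 6.8% |
| 0.10 | 1.60 | 1.265 | 12.1% | 1.140 | 8.6% |

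**4. The planned linear slope.** Visits are at months 0, 1, 2 and 8: mean 2.75, sum of squared deviations 38.75. Let the group effect be 0, 0.5u, u and Lu at these visits. Its contribution to a least-squares slope is (−1.75 × 0.5 − 0.75 + 5.25L)u / 38.75, which is 0.0935u if it persists (L = 1) and −0.0419u if it is gone by month 8 (L = 0). Let w be the within-group variance of week-8 change. Then var(u) = w × ICC / (1 − ICC), and under compound symmetry the participant slope variance is (w/2) / 38.75 = 0.0129w.

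- Effect persists: slope ICC 0.007 / 0.034 / 0.070, alpha 5.5% / 7.4% / 10.0%.
- Effect fades: slope ICC 0.001 / 0.007 / 0.015, alpha 5.1% / 5.5% / 6.0%.
- Effect persists and random slopes are half of participant slope variance (assumed). With e the residual variance in the sense w = 2e above, w becomes 2e + 4e/38.75 = 2.103e and participant slope variance 2e/38.75 = 0.0516e. The slope ICC is 0.004 / 0.018 / 0.038 and alpha 5.2% / 6.3% / 7.7%.

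**5. Waves shared by the arms.** If a share ρ of group variance is common to both active arms, the head-to-head DEFF is 1 + ICC × (m(1 − ρ) − 1). Half shared: 1.025 / 1.125 / 1.25, alpha 5.3% / 6.5% / 8.0%. Fully shared: 0.99 / 0.95 / 0.90, alpha 4.9% / 4.4% / 3.9%.

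**6. Robust standard errors without a cluster variable.** Simulated head-to-head alpha is 6.4% / 9.5% / 13.2%. It is already 5.6% at ICC 0, so about 0.6 point is small-sample error rather than clustering.

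**7. How candidate remedies behave** (simulation, 6 groups of 7 per arm, one change score or slope per participant, head to head).

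- Cluster sandwich with a normal reference: alpha 10.4% at ICC 0, or 7.9% with a G/(G − 1) correction.
- Group-mean test on 10 df, groups independent: 5.0%.
- Mixed model by REML with Satterthwaite df, groups independent: 3.4% / 3.6% / 4.3% / 4.8% at ICC 0 / 0.01 / 0.05 / 0.10.
- Group effects fully shared by wave, ICC 0.10, no wave term: group-mean 1.6%, REML 1.3%.
- Three trainer pairs per arm each leading two groups, with half the group variance at trainer level (assumed): group-mean 6.7% / 7.8% at ICC 0.05 / 0.10.

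Not simulated: the four-visit mixed model with missing visits, or quadratic growth.

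**The case against.** The strongest reply is that the impact rests on an ICC nobody has estimated. At 0.01 the excess is below one percentage point. That stands, and it is why the point is conditional.

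A reader might infer from the table that the trial's head-to-head error rate is about 12%, or 15.5% with 10 analysed members per group (DEFF = 1 + 9 × 0.10 = 1.90). The documents do not support that reading. They give no ICC; the planned contrast is a linear slope over four visits, for which the figures are lower; and 10 analysed per group contradicts the plan's own attrition assumption ("Assuming an attrition rate of about 33.5%, based on prior trials on cancer patients using qigong"). If classes are filled in waves that affect both arms equally, the head-to-head excess disappears.

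A correction can also do harm. At ICC 0.01 the REML test misses 5% by more (3.6%) than the naive test does (5.7%), and either remedy is badly conservative under fully shared waves without a wave term. So the documents do not support replacing the main analysis outright.

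Controlling for practice compliance might absorb some between-group variation. It is not a group term, however, and nothing shows how much it would absorb.

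What survives is the omission. The plan does not say how classes are filled or whether trainer pairs lead several, so no reader can tell which of these cases applies.

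**Conclusion.** The concern holds in conditional form. If change is positively correlated within delivery groups and group effects are not wholly shared across arms, the analysis as written understates standard errors, more for qigong versus mindfulness than for either arm against waitlist. Over an assumed ICC of 0.01 to 0.10 for week-8 change, the slope contrast runs from close to nominal to about twice nominal alpha; the upper end needs a persistent effect, no random slopes and independent groups.

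A reader might go further and conclude that the estimates are biased or that 189 is the wrong sample size. Neither follows: clustering of this kind affects precision, and without an ICC no other sample size can be derived. The plan should be changed, but this is not a fatal flaw. Confidence in the omission is high; confidence in its size is limited.

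**What to change.** 1. Record delivery-group ID, the trainers who led each group, and recruitment wave. State how groups are filled. If this is not captured during the trial, the analysis may not be recoverable later.
2. Pre-specify, at least as a sensitivity analysis for the active-versus-waitlist and qigong-versus-mindfulness contrasts, a partially nested analysis of change: a group effect in the active arms only, with each waitlist participant a singleton.
3. Name a small-sample method, not a plain cluster sandwich. A mixed model by REML with Satterthwaite df keeps the feature for which growth modelling was chosen, that it "allows analysis of all available data via full information maximum likelihood under missing-at-random assumption". It is mildly conservative and may need software other than Mplus. A group-mean test is simpler, but it uses only participants with the change score, and it holds 5% only when groups are independent across arms and trainers are not shared between groups.
4. Add a wave term if groups are formed by wave, and a trainer level if trainer pairs lead several groups.
5. State the assumed ICC range and report the estimated ICC with its uncertainty.

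The administrative cost is SAP text and a few recorded variables. The statistical cost is wider intervals and lower power in that analysis. For an illustrative d = 0.62 with 42 per arm (80% power under independence; a benchmark, not the plan's target), head-to-head power is 71% (REML) to 73% (group means) at ICC 0, and 53% at ICC 0.10 with either. With about 6 groups per arm the group variance is poorly estimated: REML puts it at zero in 55% of simulated trials at ICC 0 and 16% at ICC 0.10.

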In Traditional Chinese medicine, both movement-based and mind-based mind-body practices are known to have homeostatic functions to balance dysfunctional bodily systems. Examining the effects of mind-body practices on circadian cortisol rhythm may shed light on the homeostatic effect of mind-body practices on the dysregulation of the HPA system.

Clinical contributions

The clinical popularity of qigong and mindfulness meditation among local cancer survivors calls for a need for more established evidence on their benefits. Better understanding on culturally popular interventions, in particular, the common and unique effectiveness of different approaches are crucial, as patients and qualified healthcare professionals can select or provide practices which will produce maximum benefits, satisfaction, adherence, and sustainability. This study envisions bringing forth evidence-based mind-body practices which are easily learned, can be self-practiced and incorporated into patients' lifestyles.

Objectives

1. **Primary objective 1** is to study the effectiveness of Baduanjin qigong and Mindfulness mediation for Chinese colorectal cancer (CRC) patients as compared to a no-intervention control independently on:

(1) cancer-related symptoms and symptom distress

(2) mental health

(3) quality of life

(4) biomarkers

(5) mindfulness level

2. **Primary objective 2** is to examine the commonalities and differential effectiveness between two interventions on:

(1) outcome variables

(2) magnitude of change

(3) pace of change

(4) extended compliance

3. **Secondary objective** is to examine the associations between psychological, physical and psychophysical markers and how those relationships change across the time points.

Background of the research

The Reciprocity of the Mind and Body in Cancer

Colorectal cancer impairs patients on multiple levels of well-being. While most physical symptoms can be managed by medication, psychosocial stressors may arise and persist to complicate survival and reduce quality of life of survivors[19]. Patients, especially those who requiring colostomy, suffer from psychosocial trauma including depression, the fear of relapse, altered self-image, loss of social functioning and connections[20]. Local statistics further indicated a high prevalence of elevated depressive symptoms (21.8%)[21].

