The foregoing brief review suggests that mind-body practices like meditation and qigong benefit both physical and mental health albeit via different entry points. As discussed in earlier sections (Long-term impact), qigong and mindfulness meditation practices represent two very distinct approaches of mind-body practices. Although riding on the common component of focusing on breath, Chinese medical philosophies contrasted dynamic with static practices. Mind-based practices such as mindfulness meditation, relaxation or imagery are typically connoted as techniques to cultivate the mind's ability to influence bodily function and symptoms[32], by means of focused-awareness training; while movement-based practices like qigong and yoga represent another category of health practice capitalizing on movement and attention to foster such mind-body connection via the physical body, by means of mild-moderate physical exercise with inner-directed focus.

The review above is also suggestive of how most existing research on qigong and mindfulness meditation has thus far studied their effects independently, which calls for a need to provide comparative intervention research to elucidate how such contrasting approaches in mindbody practices affect the psychosocial and physiological benefits as well as compliance on patients.

Diurnal Cortisol rhythm and Cancer

The hypothalamic-pituitary-adrenal (HPA) axis activity is responsible for the body's reaction to stress and immune regulation. The dysfunction of the HPA axis in cancer patients reflected by the distortion of the diurnal cortisol rhythm is further associated with tumor characteristics and even survival[7, 46, 47]. Salivary cortisol is a neuroendocrine indicator of HPA axis. It is an established and reliable physiological marker for stress-related improvements after mindfulness and qigong practices[10, 48]. Yet, the limited handful of studies on mindfulness and qigong showed little consensus to establish its effects on cortisol patterns or levels[44, 48]. Meanwhile, a local study found a positive decreasing trend of cortisol after Baduanjin qigong with depressed elders with chronic medical illnesses[49]. Given the important implications of salivary cortisol on cancer, understanding the changes in cortisol profiles after qigong and meditation can further elucidate the linkage between mind-body practices with patients' total well-being.

Study Hypotheses

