- (f) Salivary cortisol. Salivary cortisol collection will be conducted by participants themselves. Saliva samples will be collected at 5 prescribed times (awakening, 45 minutes postawakening, 12:00pm, 5:00pm and 9:00pm) using the collection device, Salivette, which includes a cotton swab to place under the tongue. Smoking, eating and drinking should be avoided and refrained one hour prior to saliva collection. Samples collected will be kept frozen at -20°C.Daily condition measures with salivary cortisol-Measures on participants' health behaviors and activities on the day of saliva collection will be collected along with cortisol. These include (i)sleep quantity that day (hours of sleep at night and nap hours), (ii)subjective sleep quality rated on a scale of 1-10, (iii)smoking habit and the number of cigarettes that day (iv)alcohol/coffee drinking habit and the approximate amount that day, and (v)subjective evaluation of stress levels on the day of collection rated on a scale of 1-10. All the above measures will affect the diurnal cortisol rhythm and must be considered in analysis.
- (g) Blood pressure and heart rate. Following recommended procedures by the Canadian Medical Association[69], blood pressure and heart rates would be measured twice from each arm with a five minute rest intervals between measurements. The four collected readings will be averaged.
- (h) Mindfulness. The Chinese Five Facet Mindfulness Questionnaire (Short form) will be used upon permission. It has 5 domains, observing, describing, acting with awareness, nonjudging to inner experience and nonreacting to inner experience[70]. The 5-point Likert scale has 20 items.

- (i) Compliance. Participants will record their daily duration of qigong or mindfulness meditation practice over the course of the study. This will provide information on the frequency and intensity of practice, and maintenance of self-practice habits after the intervention period.
- (j) Demographics. Participants socio-demographic, such as age, gender, education level, employment status and marital status, as well as clinical profile, including cancer diagnosis, staging, treatment and medication record, onset of mood disturbances if any, critical events around the time of onset, physical exercise habits, complementary treatment used, and psychosocial support service utilization, will be documented based on self-report.

Data analyses

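### The one-hour rule before saliva sampling leaves out practice and exercise, so an acute response of unknown size and direction could be mixed into the cortisol-rhythm effect in the active arms

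*Combined protocol and SAP*

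**What the plan says.** Under Biomarkers (f), sampling is spread over the day: "Saliva samples will be collected at 5 prescribed times (awakening, 45 minutes postawakening, 12:00pm, 5:00pm and 9:00pm". It is not supervised: "Salivary cortisol collection will be conducted by participants themselves". The only stated restriction before a sample is "Smoking, eating and drinking should be avoided and refrained one hour prior to saliva collection".

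The same item adds a record of health behaviour and activity on the sampling day. The items listed are hours of sleep, sleep quality, smoking, alcohol or coffee, and stress. The plan says that these must be taken into account in the analysis.

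Under Intervention groups (a), "participants are encouraged to practice Baduanjin qigong for at least 20 minutes each day". Item (b) recommends the same minimum for mindfulness. Neither gives a time of day. Both programmes also have a 90-minute group session each week for eight weeks. The waitlist arm has no assigned practice until after the 6-month assessment.

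Item (i), Compliance, has participants log how long they practise each day. Data analyses, section 2, controls for the frequency, intensity and duration of practice when the two interventions are compared. Section 4 summarises cortisol as a mean of the five samples, an area under the curve and a two-level growth curve. It describes no term for recent practice.

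**The concern.** Theoretical contributions presents the cortisol question as the "homeostatic effect of mind-body practices on the dysregulation of the HPA system". That is a question about regulation of the daily rhythm, not about the state of a person who has just finished practising. The protocol itself gives reason to expect short-term change. It cites a relaxation response that lowers sympathetic activation, and it describes movement-based practice as working "by means of mild-moderate physical exercise with inner-directed focus".

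The exposure is not balanced by randomisation. Assigned practice exists only in the active arms and only after baseline, so any acute response enters exactly where the treatment effect is estimated. Cortisol serves all the study's objectives, so both the comparison with waitlist and the comparison between the two interventions could be affected. If the clock time of practice is not recorded, the data cannot later show which samples followed a bout.

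**Working it through.** The plan gives no figure for an acute response, so there is nothing of its own to reproduce. The check has two parts.

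**Which samples can be exposed (from the documents)**

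- Arm: qigong and mindfulness, not waitlist (Intervention groups).
- Visit: baseline precedes randomisation and is unexposed. Weeks 4 and 8 fall within the programme. The 6-month visit is exposed only in participants who are still practising (Research design).
- Sample: the awakening sample cannot follow a same-day bout, so at most 5 − 1 = 4 samples per day can.
- Records: the log is specified as daily duration, and the listed sampling-day items do not include practice. Neither is stated to show whether a given sample followed a bout.

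**How far one exposed sample can move the result (illustration)**

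Assumed, because the documents give none of these: waking at 07:00; an acute change x of 10–40% in one sample; a between-person SD of the slope of 0.04 log units per hour. A least-squares line through one day's five log values stands in for the growth curve.

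1. Sampling times in hours are 7, 7.75, 12, 17 and 21. Their mean is 64.75/5 = 12.95, and the sum of squared deviations is 144.55. The slope weight is w = (t − 12.95)/144.55, which gives −0.041, −0.036, −0.007, 0.028 and 0.056.
2. The slope shift is w × ln(1 + x), with ln 1.1 = 0.0953 and ln 1.4 = 0.3365.
   - 9 pm: 0.0557 × 0.0953 = 0.0053 and 0.0557 × 0.3365 = 0.0187 per hour.
   - 5 pm: 0.0280 × 0.0953 = 0.0027 and 0.0280 × 0.3365 = 0.0094 per hour.
3. In SD units the 9 pm shift is 0.0053/0.04 = 0.13 to 0.0187/0.04 = 0.47. This applies to one person whose 9 pm sample follows a bout.
4. The shift in the arm mean is the step 3 figure times the share affected (computed from unrounded values):

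| Share with a bout just before 9 pm (assumed) | Shift in arm mean, SD |
|---|---|
| 1/14 = 7% (practice spread evenly from 07:00 to 21:00, one-hour window) | 0.01–0.03 |
| 25% | 0.03–0.12 |
| 50% | 0.07–0.23 |

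5. The SD is a single guess, and the results scale inversely with it. At 0.02 per hour the per-person figure doubles to 0.27–0.94 SD; at 0.08 it halves to 0.07–0.23 SD.
6. The direction depends on timing and on the sign of the response. For a 10% fall, ln 0.9 = −0.105. At 9 pm the slope moves by 0.0557 × −0.105 = −0.0059 per hour. At 45 minutes after waking it moves by −0.0360 × −0.105 = +0.0038 per hour. A rise reverses both signs.
7. The daily mean of log cortisol moves by ln(1 + x)/5 per exposed sample: 0.0953/5 = 0.019 to 0.3365/5 = 0.067.

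**The case against.** The strongest reply is that daily practice is part of both interventions, so the cortisol profile of someone who practises daily may properly include that day's practice. Theoretical contributions also says that the study looks at changes before, during and after each approach. This is a legitimate choice of target. It stands as an option, but the plan does not state it, and the homeostatic framing points the other way. Recording practice times serves either choice.

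There are partial safeguards. The log could identify sampling days with no practice at all. The list of sampling-day items may not be exhaustive, and the log's layout is not shown, so the lack of a clock time is read from silence. These points soften the concern. But daily minutes do not show which samples followed a bout, and adjusting for overall compliance does not separate an acute effect from a sustained one.

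A reader might infer more than the documents support in four ways:

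- **A medium-sized bias between arms.** The upper figure of 0.47 SD applies to one affected person and rests on assumed inputs. It would apply to an arm only if every member practised just before 9 pm. Practice at varying hours can partly cancel.
- **A false fading of effect at 6 months.** That presumes that practice lapses. Continued self-practice is something the study sets out to measure.
- **The same gap for blood pressure and heart rate.** Item (g) says "blood pressure and heart rates would be measured twice from each arm with a five minute rest intervals between measurements", but it follows a cited Canadian procedure that is not available here. That procedure may govern activity beforehand, so no gap can be established.
- **A clean contrast between exertion and stillness.** Mindfulness sessions also include yoga, so any difference in acute state between the two active arms is not absolute.

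**Conclusion.** The point holds as a gap in the sampling procedure for salivary cortisol. Followed as written, the plan allows an acute exposure that differs by arm, in up to four of five samples at weeks 4 and 8, and at 6 months in those still practising. The specified records cannot separate it from the rhythm effect.

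The documents support possible bias, not demonstrated bias. They give no size or direction for an acute response. Under the assumptions listed, the shift in the arm-mean slope from the 9 pm sample runs from about 0.01–0.03 SD, if practice is spread evenly over the day, to 0.07–0.23 SD, if half of an arm practises just before sampling. All of these figures move with the assumed slope SD. The change is worth making because it costs little and practice times cannot be reliably recovered afterwards. The gap does not by itself undermine the cortisol comparison.

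**What to change.** For all three arms:

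- Add practice of the assigned technique and other exercise to the existing one-hour rule before each saliva sample.
- Collect saliva on a day without a group session.
- Add the clock time of any practice to the sampling-day form.
- Pre-specify a sensitivity analysis of the cortisol outcomes that leaves out samples taken within an hour of practice. The hour matches the existing rule; the documents do not say how long an acute response lasts, and recorded clock times would let other windows be tried.
- State whether same-day effects of practice count as part of the treatment effect on cortisol.

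The cost is a sentence in the sampling instructions, one field on an existing form, a short addition to the analysis plan and slightly less convenient scheduling for participants.
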